Based on past surveillance data, we expect about 134 index cases per study year. To demonstrate the seasonal pattern, Figure 6 shows the number of RACD events by month from 2012 to 2014. Due to capacity

limitations, not all eligible index cases received RACD. However after more staff were hired, almost all eligible index cases received RACD.

[figure not shown]

Figure 6. RACD events by month

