2: FGDs with TPE study participants	Non-index cases residing within TPE study localities, 3-7 participants per FGD, anticipate 30 TPE study localities over duration of study.	
 • Male and female participants • Residents of index household • Residents of neighboring households • Provide informed consent (participants) 	
 • Resides in RACD study locality • Refusal to participate in the Acceptability Assessment • Speaks language not understood or able to be translated to interviewer. • Age < 18 years
3: FGDs with TPE & RACD surveillance team members	All members of the surveillance team in both TPE & RACD study arms	
 • Provide informed consent 	
 • Refusal to participate

11 Cost-effectiveness assessment

The goal of the cost effectiveness assessment will be compare TPE versus RACD in terms of costs per response or incident case of as well as cost per population and case averted as measured through the difference in asymptomatic and symptomatic infections identified at the end of the intervention. Our hypothesis is that the costs of TPE versus RACD will be lower due to the cost savings from not performing a diagnostic test as well as the cases averted due to higher effectiveness to prevent future infections.

We will collect detailed expenditure data on costs of delivery of TPE and RACD interventions. Calculations will include costs for all consumables as well as staff time, which will be prospectively collected every 10th TPE or RACD event.

12 Laboratory procedures

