14.1 Study population

Overall:

Based on the most recent census data, the overall population in the 77 study localities is estimated at 211,189 individuals. However we expect that some localities will have no incident cases and therefore not receive any intervention. In the previous two transmission seasons, only 63 of the 77 localities had at least one case. Our sample size calculations are further based on the expected at-risk population within the 63 localities, or EA that had at least one case in the previous three seasons, a total of 55,928 individuals. The size of the expected at-risk within localities varies greatly, therefore we used the harmonic mean of

population size in localities with at least one case (656 per locality) to represent the effective sample size of the study in calculations of the design effect.

Target Area:

As defined above in section 4.4, the Target Area for TPE localities is defined as all individuals residing within 200m of an index case that is detected in passive surveillance and resides in a TPE study locality, with individuals residing immediately beyond 200m included if a minimum of 30 enrolled individuals is not reached within 200m. The Target Area for RACD localities is defined as all individuals residing within 500m of an index case that is detected in passive surveillance and resides in a RACD study locality. Sample size calculations for the secondary outcome measures of seroprevalence and infection prevalence are based on the population of the Target Areas.

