The sample size for the Target Area assessments is estimated from incidence in the previous transmission season, and the expected drop in incidence among those in the TPE arm; resulting in an estimated 200 index cases total with 30 individuals screened or treated in the Target Areas around each case. With 200 index cases, we expect about 6000 encounters where individuals will receive a study intervention (either TPE or RACD). Based on preliminary RACD data, we anticipate 10% of these encounters will occur in individuals who previously received an intervention during the study period (repeated or overlapping Target Areas). For the follow-up end-line seroprevalence survey, these individuals will only be sampled once. Thus the effective sample size for the seroprevalence outcome measured in the Target Area population is expected to be 5400. Of note, the first index case for each Target Area will not be included since this person's malaria exposure occurred pre-intervention.

For the follow-up end-line infection prevalence survey, index cases will also be included as they will also be at risk for subsequent infection. Thus the effective sample size for the infection prevalence outcome measured in the Target Area population will be 5400 individuals screened plus 200 index cases, or 5600 individuals.

Adherence evaluation:

Adherence will be measured on a subsample that includes only the individuals in the Target Areas surrounding the first index case in each locality. We expect that 22 localities in the TPE arm will have at least one index case, and at least 30 individuals will be assessed for DP treatment per Target Area, for a total sample of 660 individuals.

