14.2 Outcome measures

Table 6. Outcome measures

Outcome	Indicator
Primary Aim	
Incidence	Cumulative incidence of all cases (Pf infection) identified by passive surveillance in the locality subsequent to the first reported case during the study period (not including additional cases found through RACD). Cases include both locally acquired and imported infections.
Secondary aims (effectiveness)	
Exposure (seroprevalence)	Seroprevalence to markers of recent exposure using ELISA in end-line survey samples taken from residents in Target Areas near the end of the study (expected mid 2017), excluding index cases detected through passive surveillance.
Infection prevalence	Prevalence of infection by LAMP and QTNASBA testing for gametocytes in LAMP positives in end-line survey samples taken from residents in Target Areas near the end of the study (expected mid 2017), including index cases detected through passive surveillance.
Time to first local post-intervention incident case	Time to first incident local case in the Target Area subsequent to the intervention. Target Areas that receive a repeat intervention will qualify to be included again at subsequent interventions.
Proportion of imported incident cases	Proportion of imported incident cases in the locality subsequent to the first reported case will be measured through passive surveillance. Additional cases found through RACD will not be included.
Transmission potential (by genotyping)	Microsatellite genotyping will be performed on samples collected from index cases as well as secondary cases.
Secondary aims (feasibility)	
Coverage	Proportion of persons residing within approximately 200m (TPE localities) or 500m (RACD localities) of the index case who consented to participate in the study and who completed the initial procedures for their study arm (finger prick for RDT in the RACD arm, initial dose of DP in the TPE arm)
Adherence	Proportion of persons who completed 3 days of therapy among all individuals initiated on DP in the TPE arm, as assessed by pill count
Prevalence of SAEs related to treatment	Proportion of subjects experiencing SAEs deemed possibly, probably, or definitely related to DP or AL, out of the total number of subjects enrolled
Acceptability	Qualitative assessment (See Section 10)
Cost	Cost per index case-level intervention, cost per case averted.

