Based on equation 4 from Hayes and Bennett International Journal of Epidemiology 1999;28:319-32

Assumes that population is only those in the EAs that have at least one case.

Sample size calculation based on harmonic mean of population size.

Table 8. Detectable reductions in seroprevalence given varying assumptions about prevalence in the RACD arm

# Total localities with at least one index case	# localities per arm	Number assessed per locality (n)		Outcome proportion		Km (coeff of variation)	Z beta	Power
		RACD	TPE	RACD (π_0)	TPE (π_1)			
46.6	23.3	60	60	3.00%	1.35%	0.9	0.84	80%
62.3	31.2	60	60	2.40%	1.18%	0.9	0.84	80%
49.3	24.7	60	60	2.00%	0.83%	0.9	0.84	80%
50.8	25.4	60	60	1.50%	0.57%	0.9	0.84	80%

Based on equation 4 from Hayes and Bennett International Journal of Epidemiology 1999; 28:319-326

Assumes we are including only persons in the target areas in the denominator but evaluating at locality level

Assumes 3 per 100 is the background seroprevalence

Table 9. Sample sizes for primary and secondary aims.

Outcome	Result*	Actual sample size (Effective sample size, based on harmonic mean in clusters)
Primary aim		
Incidence	0.4% (RACD) vs. 0.2% (TPE)	55,928 (41,328)
Secondary aims (effectiveness)		
Exposure (seroprevalence)	2.4% (RACD) vs. 1.18% (TPE)	5400 not including index cases (3720)
Infection prevalence	n/a	5600 includes index cases
Time to first post-intervention incident case	n/a	55,928 (41,328)

Outcome	Result*	Actual sample size (Effective sample size, based on harmonic mean in clusters)
Proportion of imported incident cases	n/a	55,928 (41,328)
Transmission potential	n/a	Genotyping estimated to be performed in 800 index cases** and 35 infections from follow-up cross sectional survey
Secondary aims (feasibility)		
Coverage in TPE Arm	80% (95% CI: 77%-83%)	1782
Adherence in TPE Arm	80%	532
Prevalence of SAEs related to treatment	n/a	5400 not including index cases (3720)
Acceptability	n/a	5400 not including index cases (3720)
Cost	n/a	10 Target Areas/arm

*for some secondary outcomes, power calculations were not performed however effective sample size is shown.

** 200 index cases will be from the study area but an estimated 600 DBS that are already collected as standard surveillance from other parts of the country will also be used to characterize the background genotypes/transmission potential in Swaziland, as it relates to the transmission potential in the study areas.

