Subgroup analyses: Although there is limited power with our constrained sample size, we will describe summary measures of incidence and intervention effects for some specific subgroups of interest within our study area population. Of particular interest are those who did or did not have insecticide spraying of their household areas, strata of risk as determined by the National Malaria Control Program, and season of index case presentation.

Secondary analyses:

Assessments of secondary outcomes will also be conducted using GEE techniques to account for the clustered nature of the data collection as described above. Secondary analyses for prevalence and seroprevalence are restricted to individuals in the Target Areas who will be participating in blood testing surveys conducted towards the end of the study (expected mid 2017). As noted, for analyses of outcomes in the Target Area sample, clustering by both locality and index case area will be accounted for in the modeling approach. To account for possible contamination by proximity to another index assigned to the TPE arm, models will also include adjustment for distance to the nearest index case treated with TPE. Planned secondary analyses and hypotheses are as follows:

Hypotheses regarding the effectiveness of TPE compared to RACD:

1. Comparison of seroprevalence using antibodies to markers of recent exposure. Using the samples collected in the end-line survey near the end of the study (expected mid 2017), we expect that seroprevalence will be lower in the Target Areas receiving TPE than in those receiving RACD.
2. Comparison of prevalence of malaria infection. Using the samples collected in the end-line survey near the end of the study (expected mid 2017), we expect prevalence to be lower in the Target Areas receiving TPE than in those receiving RACD.
3. Comparison of proportion of incident cases that are imported. We expect that local transmission will be reduced by TPE and thus the proportion of subsequent cases imported will be higher in the TPE arm than in the RACD arm. This outcome will be summarized at the locality level and analyzed with locality as the unit of analysis.

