4. Comparison of time to first post-intervention incident infection. We hypothesize that time to the first post-intervention index case within the Target Area will be longer for Target Areas receiving TPE compared to those receiving RACD. Analysis for this outcome will use a standard cox proportional hazards model to estimate the time to a subsequent incident infection among individuals in the Target Area.
5. Comparison of transmission potential using genotyping. Microsatellite genotyping will be used to measure transmission potential. DNA samples for genotyping will be collected from index cases and secondary cases. Based on malaria rates in Swaziland over the past three years, we expect approximately 200 index cases over the study period and 35 infections from the follow-up cross sectional survey (1.6% prevalence in the TPE arm and 0.4% in the RACD arm). We expect transmission potential to be lower in the TPE versus RACD arm. Relatedness of infections within Target Areas and within localities will be used as a surrogate for transmission potential.

Planned Analyses of Operational Feasibility and expected findings:

1. Coverage of the intervention. The numbers and proportion of the population completing finger prick testing (if RACD arm) or receiving at least the first dose of medication (if TPE) will be calculated by arm. The proportion of the individuals living in Target Areas around an index case that receive the TPE intervention is expected to be 80% with a 95% confidence interval from 76% to 84%.
2. Adherence to TPE. In the subsample of Target Areas surrounding the first index case in each locality assigned to TPE, we will assess adherence to the 3 day regimen of DP in TPE using pill count. We expect adherence to be 80%.
3. Safety of the TPE treatment. The number and percent of individuals experiencing an adverse event will be recorded by study arm. We expect that compared to RACD, TPE will be safely administered with few or no serious adverse events related to treatment, and no difference in SAEs compared to AL based on analysis of the adverse events report forms.
4. Acceptability of the intervention. See Section 10.
5. Costs per incident infection and per population. Detailed costing will be performed in 10 Target Areas per arm. We expect that costs per incident infection and per population for implementing the TPE intervention will be no higher than for RACD, the current standard of care.

15 Advisory Committee

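### Table 9 gives 55,928 (41,328) residents as the sample for the imported proportion, which is measured on roughly 137–270 later cases in about 30–40 localities

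*Combined protocol and SAP*

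**What the plan says.** Each row of Table 9 has an actual sample size and, in brackets, an effective one based on the harmonic mean of cluster size. The imported-proportion row reads 55,928 (41,328), the same as the primary incidence row. Its result cell is n/a, and the footnote reads "for some secondary outcomes, power calculations were not performed however effective sample size is shown".

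The outcome itself is specified elsewhere:

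- Section 14.2, Table 6: "Proportion of imported incident cases in the locality subsequent to the first reported case will be measured through passive surveillance". Cases found through RACD are left out.
- Section 14.4, third secondary analysis: "This outcome will be summarized at the locality level and analyzed with locality as the unit of analysis".
- Section 3 gives a directional hypothesis, a higher imported share under TPE, with no size attached.

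The inputs for counting cases and localities are also in the plan. Section 14.1 has "resulting in an estimated 200 index cases total", and section 14.4 repeats it: "we expect approximately 200 index cases over the study period". Section 4.4 gives a higher rate: "we expect about 134 index cases per study year". On localities, section 14.1 says that "only 63 of the 77 localities had at least one case".

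**The concern.** The denominator of this outcome is cases and its unit of analysis is the locality. Residents are neither, so 55,928 cannot be its actual sample and 41,328 cannot be its effective sample. Table 9 changes unit where an outcome calls for it: transmission potential is given in index cases and infections, and cost in Target Areas. A resident count in this row is therefore not a convention of the table.

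The imported share is one of five secondary effectiveness outcomes, and section 9.4 treats it as a surrogate for the reproduction number under control. A reader who takes Table 9 at face value would believe that it rests on the same sample as the primary outcome, and could read a null result as evidence of no effect on local transmission.

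**Working it through.** **1. Reproduce the stated figures.** The expected at-risk column of Table 2, summed over the 63 localities with at least one case, gives exactly 55,928. Its harmonic mean is 656.3, and 63 × 656 = 41,328. Both entries are therefore resident counts.

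**2. Expected later cases.** Later cases = total cases − one first case per locality with a case.

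| Source of total | Later cases | 55,928 ÷ later cases | 41,328 ÷ later cases |
|---|---|---|---|
| 200 over the study (14.1, 14.4) | 200 − 63 = 137 | 408 | 302 |
| 134 a year for two years (4.4) | 268 − 63 = 205 | 273 | 202 |
| Table 2 history | 333 − 63 = 270 | 207 | 153 |

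The 137 is approximate, because it sets a 200-case projection against 63 localities observed with 333 cases. Scaling the Table 2 rates to 200 cases under a Poisson assumption gives about 46 localities with a case and about 154 later cases, which lies inside the range above.

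**3. Contributing localities.** Of the 63 localities in Table 2 with a case, 23 had exactly one, so 40 could yield a later case. Scaled to 200 cases, the number is about 32. Against 40 localities the stated figures are too large by 55,928/40 ≈ 1,400 and 41,328/40 ≈ 1,030.

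**4. Precision on the planned unit.** Assumptions: equal numbers of localities per arm (m), unweighted locality proportions, two-sided alpha of 0.05 (the plan does not state sidedness).

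- 95% half-width = 1.96 × SD × √(2/m)
- Detectable difference at 80% power = (1.96 + 0.84) × SD × √(2/m)

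The SD of the imported share across the 40 localities with two or more cases is 0.307. Table 2 does not give the order of cases, so this uses all cases in each locality. Thinning Table 2 at random to 200 cases, and dropping one case at random per locality as the first, gives an SD of about 0.35 over about 32 localities.

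| Scenario | SD × √(2/m) | Half-width | Detectable difference |
|---|---|---|---|
| 20 v 20, SD 0.307 | 0.097 | 19 points | 27 points |
| 16 v 16, SD 0.35 | 0.124 | 24 points | 35 points |

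**5. A difference to compare with.** The plan states none, so this is an illustration. The Table 2 imported share is 97/333 = 29%. If local cases were halved and imported cases unchanged, it would be 97/(97 + 118) = 45%, a shift of 16 points. Power is then Φ(0.16/0.097 − 1.96) ≈ 38% in the first scenario and Φ(0.16/0.124 − 1.96) ≈ 25% in the second.

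**The case against.** The strongest reply is that nothing depends on this cell. The result column says n/a, the footnote admits that no power calculation was made, and the text of section 14.3 discusses only incidence, seroprevalence, coverage and adherence. Section 14.4 takes the locality as the unit, so the standard error will come from localities whatever Table 9 says. This stands, and it makes the point a table correction rather than a flaw in the analysis. It does not rescue the entry, because the same footnote says that the effective sample size is shown, and for this row it is not.

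Three stronger readings are tempting, and the documents do not support them.

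- A reader might infer that the plan conceals low power or presents the outcome as powered. It does neither.
- A reader might compute a case-level design effect from Table 2, about 4.5, and conclude that the interval is near ±37 points and the detectable difference near 53. The 4.5 describes all 333 historical cases. Thinned to 200 cases it is about 3.2, it depends heavily on a few localities with many imported cases, and a case-level comparison is not the planned analysis. Nor is it established that no plausible effect could be detected. If the whole 50% fall in incidence came from local cases, the imported share would go from 29% to 29/0.50 = 58%. That 29-point shift lies within the 27 to 35 point range.
- A reader might infer that the acceptability row has the same fault. Refusal is a person-level measure and section 6.1 describes refusals as rare, so about 5,400 is a fair approximation to the number approached. The focus-group sample is already in Table 5: "3-7 participants per FGD, anticipate 30 TPE study localities over duration of study".

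**Conclusion.** The sample size stated for the imported proportion is wrong in kind. The figures are correctly computed resident counts placed against an outcome measured on later cases and analysed by locality. The overstatement is about 150- to 400-fold against later cases and about 1,000-fold or more against localities. The exact multiple depends on which of the plan's case projections is used and on whether the actual or the effective figure is compared.

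The precision figures assume that Table 2's between-locality spread carries over to the trial and that contributing localities divide equally between arms. If TPE leaves fewer localities with a later case, the interval would be wider. On these assumptions the outcome can give an estimate with a wide interval but could not reliably detect a shift of about 16 points. The size of any true shift is not stated in the plan.

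**What to change.** In Table 9, replace 55,928 (41,328) in the imported-proportion row with:

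- the expected later cases as a range, about 137 to 270, naming the projection behind each end;
- the localities expected to contribute: 40 of 63 on Table 2 counts, about 32 if cases fall to 200.

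Add the expected locality-level precision, about ±19 to ±24 points, and the detectable difference of about 27 to 35 points, with the SD and the split of localities assumed. Amend the footnote so that it no longer says the effective sample size is shown for this row. In section 14.4, say that the outcome will be reported as an estimate with its confidence interval and that a null result will not be read as evidence of no effect.

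The cost is a table and wording change. It needs no new data and no change to the design or the analysis unit, though the sample printed for this outcome becomes much smaller.

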14.4 Analytical plan

Preliminary Analyses and Missing Data:

One-way frequency tables for all categorical variables and distributions, ranges, and outliers for continuous variables will be generated to perform range checks, quantify the amount of missing data, and yield valuable descriptive findings that will characterize coverage and cluster and Target Area characteristics in the study population. These analyses will also be stratified by randomization group (i.e., TPE vs RACD) using cluster-based two-group comparison methods (e.g., Rao-Scott chi-square) to check the equality of group covariates at baseline. Although we expect the randomization to produce balanced covariate structures, we will consider methods of adjustment to balance baseline covariates should there be significant differences between the TPE and RACD groups. To look for areas where there is a possibility of contamination by proximity of index cases assigned to different arms, we will describe the distances between TPE and RACD assigned index cases as well as the number of RACD assigned index cases who were within 2km of an index case assigned to TPE.

Primary Analysis:

For the primary analysis comparing incidence between the TPE and RACD arms, we will follow an intention-to-treat (ITT) approach. We hypothesize that cumulative incidence in the TPE localities will be lower than in the RACD assigned localities. For the initial ITT analyses, estimates of effect will be unadjusted for any variables other than intervention group. To check for possible contamination of effects by proximity to an index case treated with TPE, a second set of ITT analyses will be conducted adjusting for intervention group and distance of index case from an index case assigned to TPE. Outcomes are assessed at the individual level. Because of the clustered nature of the data, our modeling approach will also adjust for correlation of observations by locality for analyses using the overall sample and by locality and index case for analyses using the Target Area sample. Generalized estimating equations (GEE) will be used to perform the proposed primary analyses. GEE accounts for the correlation of persons within clusters and localities. GEE estimates are consistent even if the correlation structure is miss-specified, though GEE's statistical efficiency improves as the working correlation structure more closely approximates the actual correlation structure. Thus, several working correlation structures suitable for the study's design will be considered (e.g., unstructured, Autoregressive order 1, exchangeable). The QIC statistic will be used to select the final working correlation structure. Robust Huber-White "sandwich" standard errors will be used to obtain correct inferences even if

the chosen correlation structure remains slightly miss-specified. Alpha will be set at 0.05 for all planned comparisons.

Should the preliminary analyses reveal an imbalance in the baseline covariates between the TPE and RACD arms, a second set of models will be run for all primary analyses. Adjusted models will reweight the data (through inverse probability weighting, or targeted minimum loss based estimation) to recover effect estimates that reflect an equal distribution of baseline covariates.

Subgroup analyses: Although there is limited power with our constrained sample size, we will describe summary measures of incidence and intervention effects for some specific subgroups of interest within our study area population. Of particular interest are those who did or did not have insecticide spraying of their household areas, strata of risk as determined by the National Malaria Control Program, and season of index case presentation.

Secondary analyses:

Assessments of secondary outcomes will also be conducted using GEE techniques to account for the clustered nature of the data collection as described above. Secondary analyses for prevalence and seroprevalence are restricted to individuals in the Target Areas who will be participating in blood testing surveys conducted towards the end of the study (expected mid 2017). As noted, for analyses of outcomes in the Target Area sample, clustering by both locality and index case area will be accounted for in the modeling approach. To account for possible contamination by proximity to another index assigned to the TPE arm, models will also include adjustment for distance to the nearest index case treated with TPE. Planned secondary analyses and hypotheses are as follows:

Hypotheses regarding the effectiveness of TPE compared to RACD:

1. Comparison of seroprevalence using antibodies to markers of recent exposure. Using the samples collected in the end-line survey near the end of the study (expected mid 2017), we expect that seroprevalence will be lower in the Target Areas receiving TPE than in those receiving RACD.
2. Comparison of prevalence of malaria infection. Using the samples collected in the end-line survey near the end of the study (expected mid 2017), we expect prevalence to be lower in the Target Areas receiving TPE than in those receiving RACD.
3. Comparison of proportion of incident cases that are imported. We expect that local transmission will be reduced by TPE and thus the proportion of subsequent cases imported will be higher in the TPE arm than in the RACD arm. This outcome will be summarized at the locality level and analyzed with locality as the unit of analysis.
4. Comparison of time to first post-intervention incident infection. We hypothesize that time to the first post-intervention index case within the Target Area will be longer for Target Areas receiving TPE compared to those receiving RACD. Analysis for this outcome will use a standard cox proportional hazards model to estimate the time to a subsequent incident infection among individuals in the Target Area.
5. Comparison of transmission potential using genotyping. Microsatellite genotyping will be used to measure transmission potential. DNA samples for genotyping will be collected from index cases and secondary cases. Based on malaria rates in Swaziland over the past three years, we expect approximately 200 index cases over the study period and 35 infections from the follow-up cross sectional survey (1.6% prevalence in the TPE arm and 0.4% in the RACD arm). We expect transmission potential to be lower in the TPE versus RACD arm. Relatedness of infections within Target Areas and within localities will be used as a surrogate for transmission potential.

Planned Analyses of Operational Feasibility and expected findings:

1. Coverage of the intervention. The numbers and proportion of the population completing finger prick testing (if RACD arm) or receiving at least the first dose of medication (if TPE) will be calculated by arm. The proportion of the individuals living in Target Areas around an index case that receive the TPE intervention is expected to be 80% with a 95% confidence interval from 76% to 84%.
2. Adherence to TPE. In the subsample of Target Areas surrounding the first index case in each locality assigned to TPE, we will assess adherence to the 3 day regimen of DP in TPE using pill count. We expect adherence to be 80%.
3. Safety of the TPE treatment. The number and percent of individuals experiencing an adverse event will be recorded by study arm. We expect that compared to RACD, TPE will be safely administered with few or no serious adverse events related to treatment, and no difference in SAEs compared to AL based on analysis of the adverse events report forms.
4. Acceptability of the intervention. See Section 10.
5. Costs per incident infection and per population. Detailed costing will be performed in 10 Target Areas per arm. We expect that costs per incident infection and per population for implementing the TPE intervention will be no higher than for RACD, the current standard of care.

15 Advisory Committee

